## 10.6 Restrictions during the study

### 10.6.1 General restrictions

Unprotected sexual contact with new male partner will not be allowed during the study to avoid chlamydia symptoms being similar to UTI symptoms.

The subject must be willing and able to comply with the instructions for storage of the IP given (see Section 11.3).

### 10.6.2 Prior and concomitant therapy

No probiotic food supplements, probiotic foods or fermented food other than the test product, including vaginal products containing *Lactobacillus* (including probiotic tampons) or affecting the pH, are allowed from screening and throughout the study period.

Neither is any food or food supplements containing cranberries allowed from screening and throughout the study period. Subjects should continue with the same general diet and lifestyle, except probiotic and cranberry consumption.

Use of spermicide contraceptives including spermicidal condom will not be allowed during the study, up to Day 180.

Use of oral or vaginal fungicides will not be allowed during the study, up to Day 180. If typical vaginal candida symptoms appear (itching and typical thick, clumpy, white vaginal discharge) sporadic usage of oral fluconazole 150 mg as a single dose may be allowed and should be noted.

Subjects must not participate in any other clinical interventional study during the study period.

Other medications considered necessary for the subject's safety and well-being, may be used during the study period. In case of antibiotic use, the type and duration should be recorded. Any use of fluconazole, prohibited medication, therapies or products will require evaluation by the Investigator to determine whether or not the subject should continue in the study. This may be done in consultation with the Sponsor.

## **10.7 Criteria for subject withdrawal**

Subjects are free to discontinue their participation in the study at any time and for whatever reason without affecting their right to an appropriate follow-up assessment or their future care. If possible, the reason for withdrawal of consent should be documented.

Subjects may be discontinued from the study at any time at the discretion of the Investigator for any of the following reasons:

- Severe non-compliance to Study Protocol procedures, as judged by the Investigator and/or Sponsor.
- Subject is lost to follow-up.
- Significant AEs posing a risk for the subject, as judged by the Investigator and/or Sponsor

### **10.7.1 Procedures for discontinuation of a subject from the study**

A subject who prematurely discontinues participation in the study will always be asked about the reason(s) for discontinuation and the presence of any AEs. If possible, they will be contacted by the Investigator and assessed according to the procedures scheduled for the follow-up assessment, as far as possible. Any ongoing AEs will be followed as described in Section 12.5.6.

All data collected until discontinuation will be used in the study.

### **10.7.2 Subject replacement**

Withdrawn subjects will not be replaced.

## **10.8 Randomization**

Subjects will be randomized to treatment with active test product or placebo (1:1). A computer-generated randomization list will be created by CTC AB. The randomization will be performed using block randomization within each IP distribution site (these sites will be identified by the Sponsor prior to creating the randomization list). Each distribution site will receive pre-packed boxes with either the test product or placebo, each box marked with a randomization number dedicated to the subject at randomization. The clinic will have a sub-part of the randomization list which contains information about randomization number and distribution site.

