## 10 STUDY POPULATION

### 10.1 Recruitment

Study subjects will be recruited using advertisement (*e.g* in social media, at pharmacies etc.) directed to pre-defined regions surrounding a number of IP distribution points.

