## **11.3 Conditions for storage**

The IP should be stored at +2 to +8°C. Temperature control will be performed once daily at the distribution sites (business days only). When the IP has been distributed to the subject, it should be refrigerated as soon as possible and kept in the refrigerator until use. A thermal bag will be provided to each subject. The product can be stored in the thermal bag for a maximum of 12 hrs.

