## 16.5 Analysis of primary endpoint

The primary endpoint will be the mean number of confirmed UTIs during six months from start of intervention, as compared to placebo.

The mean number of UTIs per intervention group will be estimated based on the total number of UTIs by subject.

The mean number of UTIs will be analysed using analysis of covariance with intervention, UTI history, age, and sexual activity as independent variables. No intervention by centre interaction will be possible to apply in this analysis. The estimated intervention difference will be presented by LSMeans and a 95% confidence interval.

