### **16.8.3 Multi-centre studies**

No adjustment for centre will be applied, since this will not be considered as a multi-centre study.

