7.1.1 Main analytical approach

The mean number of UTIs will be analysed using analysis of covariance with intervention, UTI history and age as independent variables. Sexual activity will only be used in the analysis if it is possible.

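### Randomisation is blocked within IP distribution site, but no efficacy analysis includes site, so if UTI frequency differs between sites the primary ANCOVA reports a slightly too wide interval and a conservative test

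*Protocol*

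**What the plan says.** Protocol 10.8 allocates 1:1 and adds: "The randomization will be performed using block randomization within each IP distribution site". The sponsor names the sites before the list is made, and the clinic's part of the list carries each randomisation number with its distribution site. There is more than one such site: Protocol 10.1 describes advertising "directed to pre-defined regions surrounding a number of IP distribution points".

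No efficacy model uses the site:

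- **Primary and secondary UTI counts.** Protocol 16.5 plans "analysis of covariance with intervention, UTI history, age, and sexual activity as independent variables". SAP 7.1.1 has "analysis of covariance with intervention, UTI history and age as independent variables", with sexual activity added only if possible. SAP 7.2.3 repeats this for the secondary counts.
- **Time to first relapse.** Protocol 16.6.2 and SAP 7.2.1.2 name Cox regression without strata.
- **Relapse proportions.** Protocol 16.6.3 and SAP 7.2.1.3 name a chi-square test without strata.

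On centre, Protocol 16.8.3 says: "No adjustment for centre will be applied, since this will not be considered as a multi-centre study". SAP 4.9 repeats the sentence. SAP section 8, which lists changes from the protocol, does not add site.

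**The concern.** The stated reason for not adjusting is that one study site runs the trial. That describes where outcomes are collected. It leaves open why a factor used to constrain the allocation is absent from the analysis.

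When arms are balanced within strata, differences between strata largely cancel out of the treatment comparison, so the true variance of the estimated difference falls. A model without strata still counts those differences as residual noise. Its standard error is then larger than the true one, its interval too wide, and its test runs below the nominal 5%. Regional recruitment around each distribution point is a plausible route to site differences in UTI frequency, although the documents do not show that any exist.

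What is at stake is precision and a clean pre-specification. If a reader later asks for the stratified analysis, the choice of model will be made after the data are known.

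**Working it through.** **Inputs from the documents (Protocol 16.1, 16.2):** means 0.75 and 1.35, so a difference of 0.60; SD 1.15; two-sided 5%; 80% power; 118 evaluable women; 15% dropout; 140 included.

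**Inputs not in the documents, assumed:** number of sites, block size, and the share ρ of outcome variance that lies between sites. In the model as planned, ρ is the share left after UTI history and age.

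**1. The plan's own figure.** The normal approximation gives 58 per arm (116). The noncentral t gives 59 per arm (118) with power 80.2%, matching the stated 118. Then 118/0.85 = 138.8, or 139, which becomes 140 with equal arms.

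**2. Closed form, 59 per arm, 8 sites, near-perfect balance within site.** The nominal standard error is 1.15 × √(2/59) = 0.212, so the standardised difference is 0.60/0.212 = 2.83.

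- Inflation of the reported standard error: 1/√(1−ρ).
- Actual type I error without site: 2 × [1 − Φ(1.96/√(1−ρ))].
- Power without site: Φ((2.834 − 1.981)/√(1−ρ)), where 1.981 is the t critical value on 116 df.
- Power with site: noncentral t on 109 df (118 − 8 − 1), with SD 1.15 × √(1−ρ).

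| ρ | SE too large by | Type I error without site | Power without site | Power with site |
|---|---|---|---|---|
| 2% | 1.0% | 4.8% | 80.6% | 81.0% |
| 5% | 2.6% | 4.4% | 80.9% | 82.2% |
| 10% | 5.4% | 3.9% | 81.6% | 84.2% |

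At ρ = 10%, for example, 1.96/√0.90 = 2.066, and the two-sided tail beyond it is 3.9%. At ρ = 0, adjusting for 8 sites leaves power at 80.2%.

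**3. Simulation with imperfect balance.** Settings: 118 women spread at random over 5, 10 or 20 sites, permuted blocks of 4 within site, normal outcomes, 4,000 runs per setting. Ranges are across the three site counts.

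| ρ | Type I error without site | Type I error with site | Interval without site relative to with site | Power without site | Power with site |
|---|---|---|---|---|---|
| 0 | 5.0–5.3% | 4.8–5.3% | 0.98–1.00 | 79–80% | 78–80% |
| 2% | 4.5–5.1% | 4.5–5.5% | 0.99–1.01 | 79–81% | 78–80% |
| 5% | 3.9–4.5% | 4.3–4.9% | 1.01–1.02 | 80–82% | 80–83% |
| 10% | 3.6–4.1% | 4.6–4.8% | 1.04–1.05 | 81–83% | 83–85% |
| 20% | 2.7–3.6% | 4.4–5.2% | 1.09–1.10 | 82–85% | 87–89% |

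The Monte Carlo standard error of a 5% rejection rate here is √(0.05 × 0.95/4000), or about 0.3 points, so small differences in type I error are noise.

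**4. Where adjusting costs something.** With 20 sites and ρ of 0 or 2%, power is 79.1% or 79.3% without site and 77.9% with it. The adjusted interval is about 1% to 2% wider.

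**5. Scope.** These figures are for the ANCOVA. For the unstratified chi-square test the same omission gives a conservative p-value. For the Cox model it mainly pulls the hazard ratio somewhat towards 1.

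**The case against.** The strongest reply is that little is at risk. The error is conservative, planned power is kept, and adjusting gains 0.4, 1.3 and 2.6 points of power at ρ of 2%, 5% and 10%. Distribution sites are where women collect product. Outcomes come from one clinic asking the same questions by phone or video, so ordinary differences in assessment between centres do not arise. With many small sites and little variation between them, fixed site terms lose slightly more than they gain. All of this stands, and it limits the weight of the point. It does not supply a reason for omitting the stratum, because the plan's reason concerns centres.

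A reader might infer more than the documents support:

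- **That false positives are inflated or the trial is underpowered.** The calculations show the reverse: type I error at or below about 5%, and power near or above 80% without site.
- **That the balance from stratifying is thrown away.** It is not. The true variance of the unadjusted difference still falls, which is why power without site rises with ρ. Only the reported standard error misses it.
- **That cold storage at the sites makes site adjustment necessary.** Only the test sachet contains bacteria (Protocol 11.1.1, 11.1.2), so differences in storage would act mainly in the active arm. That is an intervention-by-site interaction, which an additive site term does not model. Regional recruitment is the better support for a site main effect.
- **That the plan expressly forbids a distribution-site term.** Protocol 16.8.3 and SAP 4.9 speak of centre. Distribution site is absent because no model lists it.

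**Conclusion.** The point holds as a modest, conservative inefficiency. The trial randomises within distribution site and analyses without it, and the stated reason does not bear on that stratification. If site shares of variance are 2% to 10%, the ANCOVA standard error is about 1% to 5% too large and the type I error about 4.8% down to 3.9%. If sites do not differ, the planned analysis loses nothing.

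These sizes rest on assumed values for the number of sites, the block size and the between-site variance, and on approximately normal outcomes. The documents give no evidence that UTI frequency varies by site. The case for changing the plan is that the analysis should follow the allocation scheme, that the variable is already recorded, and that the choice should be fixed before unblinding.

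**What to change.** In SAP 4.9, 7.1.1 and 7.2.3, state along these lines:

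*IP distribution site is a randomisation stratum. It will be included in the primary and secondary UTI-count ANCOVAs as a fixed term, with small sites pooled by a rule set before unblinding, or as a random effect if there are many small sites. Using the same pooled sites, the Cox model will be stratified by site and relapse proportions will be compared with a Cochran-Mantel-Haenszel test.*

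The pooling rule should give a minimum number of women per site and say how small sites are combined. The choice between fixed and random should be tied to the number and size of sites, which can be read without the treatment codes. If the sponsor prefers to leave site out, the SAP should give a reason that addresses the stratified allocation.

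Cost: a few degrees of freedom; some information lost in the Cox and Cochran-Mantel-Haenszel analyses where all or none of the women in a small stratum relapse; and a documented change, either listed in SAP section 8 as a departure from the protocol or made by amending Protocol 16.8.3 under the procedure in Protocol 13.5. No new data are needed.

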## **10.9 Blinding**

This is a double-blinded study. All study staff, including the Principal Investigator and the persons performing the subject assessments using the video link or phone calls, will be blinded during the study. Sealed individual treatment code envelopes will be kept at the clinic to be able to break the code if any emergency occurs, as judged by the Investigator.

## **10.10 Emergency decoding of blinded intervention during the study**

The intervention code may only be broken by the study medical staff in case of emergency when knowledge of the intervention received is necessary for the proper medical management of the subject. The code breaking procedure should be carefully documented in the medical records.

# **11 INTERVENTIONS**

## **11.1 Identity of Investigational Products**

The manufacturer of the IP is Inpac in Lund AB, Lund, Sweden. The two IPs (test product and placebo) each contains two sachets.

### **11.1.1 Test product**

Sachet 1 – instant drink: Xylitol, Monosodium Citrate, Cranberry Aroma, Cranberry Extract, Grape-skin Extract, Xanthan Gum, Acesulfame Potassium and Zinc Gluconate.

Sachet 2 – probiotic mix: Maltodextrin, *Lactobacillus reuteri* DSM 16666 and *Lactobacillus reuteri* DSM 17938.

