The main pharmacological treatments of cystitis usually involve the use of antibiotics, in particular pivmecillinam, nitrofurantoin or trimethoprim . Quinolones (such as ciprofloxacin and levofloxacin), fosfomycin, second-generation and third-generation cephalosporins, and b-lactam antibiotics associated with b-lactamase inhibitors  may also be used. Because of the formation of bacterial biofilms, unfortunately, the results of antibiotic treatment are often not satisfying. In fact, the infection is not always eradicated and bacteriuria and recurrences may persist . Additionally, the inadequate use of antibiotics in terms of type and duration has been a common practice, generating a continuous increase in bacterial resistance and diverse complications associated to with this indiscriminate use .

As alternatives or in addition to traditional treatments, there are some natural ingredients with a recognized effectiveness in counteracting the onset, persistence, or propagation of a UTI caused by *E. coli*. One example is the use of a dry extract of cranberry (*Vaccinium macrocarpon*), which is able to establish a natural physical-mechanical contrast against the adhesion of *E. coli* to the surface of the epithelial cells of the bladder and urinary tract . Its main activity is related to the proanthocyanidin (PAC) fraction containing oligomers that compete with the adhesions located on type-P fimbriae (FimH, mannose-sensitive) used by *E. coli* to mediate its anchorage to the epithelial cells . The profile of cranberry bioactives is distinct from that of other berry fruits, as they are rich in A-type PACs in contrast to the B-

type PACs present in most other fruit. However, clinical studies of prevention of UTI using cranberry substances are contradictory (as reviewed by Liska, et al 2016).

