## 7.2 Investigational Product

### 7.2.1 Product characteristics

*Lactobacillus reuteri* bacteria are active and multiply along the entire digestive tract and in addition, it has been shown that orally administered *L. reuteri* after the passage of the gastrointestinal (GI) tract can colonise the vagina and by that modulate the vaginal microbiota in a positive manner.

The Investigational Product (IP) consists of a combination of two *L. reuteri* strains: DSM 16666 and DSM 17938 (5x10^8 colony forming units [cfu]). The dose has been defined based on data from clinical trials performed with the two individual strains (see Section 7.2.2).

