## 8 STUDY OBJECTIVES AND ENDPOINTS

### 8.1 Primary objective

The primary objective is to evaluate the effect of oral supplementation with *Lactobacillus reuteri* on the frequency of confirmed UTI during six months from start of intervention in adult women with recurrent UTI.

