### **11.1.2 Placebo**

Sachet 1 – instant drink: Xylitol, Monosodium Citrate, Cranberry Aroma, Grape-skin Extract, Xanthan Gum and Acesulfame Potassium.

Sachet 2 – maltodextrin: Maltodextrin.

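### The test product also contains cranberry extract and zinc gluconate, which placebo lacks, so a difference between the arms cannot be attributed to L. reuteri

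*Protocol*

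**What the plan says.** **The question asked.** Protocol 8.1 sets out to "evaluate the effect of oral supplementation with *Lactobacillus reuteri* on the frequency of confirmed UTI during six months". The secondary objectives in 8.2 and the objectives in SAP 3.1 also name *L. reuteri* alone. The hypotheses in Protocol 16.2 and SAP 3.3 call the test arm the Probiotic group. The rationale in 7.3 presents the study as the first randomized trial of the two strains in combination for UTI prevention.

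**The product as described.** Protocol 7.2.1 states: "The Investigational Product (IP) consists of a combination of two" *L. reuteri* strains. It mentions no other component.

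**The product as composed.** Protocol 11.1.1 gives the test Sachet 1 as xylitol and monosodium citrate followed by "Cranberry Aroma, Cranberry Extract, Grape-skin Extract, Xanthan Gum, Acesulfame Potassium and Zinc Gluconate". Protocol 11.1.2 gives the placebo Sachet 1 as the same two ingredients followed by "Cranberry Aroma, Grape-skin Extract, Xanthan Gum and Acesulfame Potassium". Sachet 2 holds maltodextrin plus the two strains in the test arm; for placebo it is listed as "Sachet 2 – maltodextrin: Maltodextrin". The synopsis repeats both lists without any difference.

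**Cranberry elsewhere in the protocol.** Section 7.1 says that "there are some natural ingredients with a recognized effectiveness in counteracting the onset, persistence, or propagation of a UTI caused by" *E. coli*, and gives dry cranberry extract as an example. It then adds that clinical prevention studies of cranberry contradict each other. Section 10.6.2 rules: "Neither is any food or food supplements containing cranberries allowed from screening and throughout the study period".

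**The concern.** The objective names one ingredient, but randomization assigns a package of three differences: the two strains, cranberry extract and zinc gluconate. An effect of any of them would show up as a difference between the arms.

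Cranberry extract is hard to treat as an inert excipient, because the protocol itself describes an anti-adhesion mechanism for it against *E. coli* and gives 86% as the share of UTIs that are acute uncomplicated *E. coli* cystitis. Flavour matching does not explain the difference either, since both arms receive cranberry aroma and only the test arm receives the extract. The dietary restriction sharpens the contrast: cranberry is withheld from everyone outside the product, then supplied for 90 days to one arm through the product.

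At stake is the meaning of a positive primary result. Under the stated objective it would be read as evidence for *L. reuteri*, although part or all of it could come from the other ingredients.

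**Working it through.** **1. Composition, side by side (Protocol 11.1.1 and 11.1.2)**

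| Component | Test | Placebo |
|---|---|---|
| Xylitol, monosodium citrate, cranberry aroma, grape-skin extract, xanthan gum, acesulfame potassium | yes | yes |
| Maltodextrin | yes | yes |
| *L. reuteri* DSM 16666 and DSM 17938 | yes | no |
| Cranberry extract | yes | no |
| Zinc gluconate | yes | no |

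**2. Identification.** Allocation is 1:1 to two arms (Protocol 10.8). There is no arm with the test Sachet 1 alone and no factorial structure. Write the arm difference as Δ = (effect of *L. reuteri*) + (effect of cranberry extract and zinc) + (any interaction). The trial estimates Δ only. The extra ingredients coincide exactly with allocation, so covariates in the ANCOVA (UTI history, age, sexual activity) and restriction to the per-protocol set leave Δ undivided. Reading Δ as the *L. reuteri* effect requires the other terms to be zero.

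**3. The plan's sample size (Protocol 16.2).** Inputs: means 0.75 and 1.35, so a difference of 0.60; SD 1.15; two-sided 5%; power 80%.

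- Normal approximation: n per arm = 2 × (1.960 + 0.842)² × 1.15² / 0.60² = 57.7, rounded up to 58 (116 in total).
- Two-sample t-test: 58.64, rounded up to 59 per arm, or 118 in total. This is the stated figure.
- Dropout: 118 / 0.85 = 138.8, so 139; the plan has 140. Conversely 140 × 0.85 = 119.

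The arithmetic of the plan is sound. The defect is in what the comparison is said to measure.

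**4. How often a claim for *L. reuteri* would be wrong.** Suppose *L. reuteri* has no effect and the other ingredients lower the six-month mean by d. The values of d are assumptions, running up to the full design difference of 0.60. The standard error of the difference at 59 per arm is 1.15 × √(2/59) = 0.212. The noncentrality is d / 0.212, and the test is a two-sided 5% t-test on 116 degrees of freedom.

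| Assumed d | Noncentrality | P(significant), 59 per arm | P(significant), 70 per arm |
|---|---|---|---|
| 0 | 0 | 5% | 5% |
| 0.15 | 0.71 | 10.8% | 12.0% |
| 0.30 | 1.42 | 29.0% | 33.5% |
| 0.45 | 2.13 | 55.9% | 63.3% |
| 0.60 | 2.83 | 80.2% | 86.5% |

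The normal approximation at 59 per arm gives almost the same: 10.9%, 29.4%, 56.6% and 80.9%. The 5% error rate applies to a statement about *L. reuteri* only in the first row. A larger trial would make the misattribution more likely.

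**The case against.** The strongest reply has four parts.

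- **The comparison is valid and the hypotheses are testable.** Randomization gives an unbiased contrast of test product with placebo, and Probiotic group can be read as an arm label. A null result would still bear on *L. reuteri*, unless another ingredient masked a benefit. This stands. It means that H0 and H1 need relabelling only. The attribution is still made in the title, the objectives, the rationale and 7.2.1.
- **The evidence on the extra ingredients is thin.** The protocol calls the clinical cranberry studies contradictory, says nothing of zinc activity against UTI, and gives no amount for either. This also stands: the zinc point rests only on the unexplained difference in composition. But contradictory evidence leaves the cranberry effect uncertain, whereas the attribution needs it to be zero. No passage supports zero or explains the imbalance.
- **The magnitude is illustrative.** The range is assumed, its top end gives the whole design effect to the other ingredients, and the calculation ignores covariate adjustment. This is fair; the table shows a sensitivity and does not estimate a bias. For very small d the error rate stays close to 5%.
- **The composition is disclosed and no conclusion has been written in advance.** Both are true. But a result is read against its objective, and this one names *L. reuteri* alone. The list of changes in SAP 8 does not address the matter.

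**Conclusion.** The concern holds and must be fixed. The trial identifies the effect of the combination product against placebo; it does not identify the effect of *L. reuteri*. This follows from the ingredient lists and the two-arm design, and needs no assumption about whether cranberry or zinc works. Its numerical consequence does depend on an assumption. With no effect of *L. reuteri*, the chance of a significant primary result is 5% if the other ingredients are inert, and rises through 11%, 29% and 56% to 80% as their assumed effect goes from 0.15 to 0.60 UTIs per six months (unadjusted t-test, 59 per arm, SD 1.15). The case for cranberry rests on the protocol's own background and dietary restriction; the case for zinc rests only on composition. No change in analysis can repair the attribution.

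**What to change.** Reconcile the title, the synopsis and Protocol 7.2.1, 7.3, 8.1, 8.2 and 16.2, together with SAP 3.1 and 3.3, with Protocol 11.1.

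- Describe the product by its full composition.
- State the objectives and hypotheses for the combination product (*L. reuteri* DSM 16666 and DSM 17938 with cranberry extract and zinc gluconate) against placebo.
- Record the change in SAP 8, and state there and in the report that no effect can be attributed to *L. reuteri* alone.

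This is enough to make the conclusion correct. It costs document wording and a narrower, less favourable claim. The 118 evaluable and 140 randomized subjects, the endpoint and the ANCOVA are unchanged. SAP version 1 is dated August 2019, after the protocol's estimated completion in Q4 2018, so rewording is probably the only remedy still open for this trial.

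A claim for *L. reuteri* alone would need a Sachet 1 that is the same in both arms; whether to pursue that is the sponsor's choice. The 0.60 difference would then have to be justified for the strains alone. If 25%, 50% or 75% of it (assumed shares) belonged to the other ingredients, the remaining difference would be 0.45, 0.30 or 0.15. Power at 59 per arm would then be 56%, 29% or 11%. By the normal formula above, 80% power would need 206, 462 or 1,846 evaluable subjects.
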